## **6.2 Intervention Administration**

Treatment will be administered on an outpatient basis. Patients will be randomized 1:1 basis to either MGE or placebo. The study is double-blind and the patients will take 4 capsules by mouth twice daily.

## **6.3 Investigational Agent**

This study uses a specific formulation of MGE produced by Piedmont Research & Development Corporation from a powdered extract obtained from NPC Corporation, formerly known as Nature's Pearl (Advance, NC). The same product was used for a phase 1 study in advanced cancer patients and the on-going Phase 2 study in prostate cancer patients (FDA IND 128937; FDA IND 139288). The muscadine grapes are pressed and processed on site per good manufacturing practice (FDA Code of Federal Regulations 21). The extract is dissolved in water, dried and converted to powder at Pharmachem Laboratories, Inc. (Kearny, New Jersey). The MGE is encapsulated with a vegetable capsule of hypromellose, bottled and labeled at Clinical Encapsulation Services (CES) (Schenectady, NY). Quality control testing for microbial contamination and phenolic levels occurs numerous times during the production process and will continue at regular intervals until study completion. The MGE will be tested biannually for total phenolics using the Folin-Ciocalteu method, with gallic acid as the standard, and microbes will be assessed annually by American Testing Lab (San Diego, CA). MGE will be dispensed by the WFBCCC Investigational Drug Studies Pharmacy which managed the Phase 1 and on-going Phase 2 study.

## **6.4 Placebo Description**

Placebos will be supplied by Clinical Encapsulation Services (CES) (Schenectady, NY), an FDA-registered facility, registration number 16691092818. The capsules contain microcellulose tinted to match MGE and are encapsulated with a vegetable capsule of hypromellose of the same size as the MGE capsules. Placebo were bottled and labeled by CES. Quality control testing for microbial contamination (aerobic count, yeast and mold, E.coli/coliform, staph aureus, enterobacteriaceae, and salmonella) and phenolic level (to ensure no cross contamination) occurs during the production process. Stability testing for microbial contamination and content uniformity will continue at regular intervals.

**Storage requirements:** Capsules should be stored at room temperature.

**Route of administration:** Placebo is available for oral administration.

## **6.5 General Concomitant Medication and Supportive Care Guidelines**

If participants start Coumadin/Warfarin while on study, we will advise them of the potential interaction with MGE. Participants who start Coumadin/Warfarin while on study will be asked to stop dosing study drug (see section 6.7 regarding indications for discontinuation of intervention). Participants will be instructed to inform their prescribing providers of the recommendation to recheck within 7 days of starting medication and again within 7 days of completing our study drug.

## **6.6 Study Assessments**

All in-person study-related activities will occur at the Wake Forest Baptist Medical Center Clinical Research Unit, or at the High Point, Wilkes, or Statesville clinic sites and do not need to be coupled with standard-of-care clinic visits.

### **6.6.1 Vitals signs, performance status**

Vital sign assessment consists of heart rate, blood pressure, respiration rate, temperature. Height and weight will be collected at baseline with weight repeated at follow-up.

Performance status will be assessed at baseline using the Karnofsky Self-Reported Performance Rating Scale (KPS).

### **6.6.2 Laboratory assessments (safety)**

The following laboratory studies will be obtained at follow-up:

- Complete blood count (CBC) with differential: Total white blood cell count (WBC) with differential, hemoglobin/hematocrit, and platelet count.
- Blood chemistry (CMP): Sodium, Potassium, Chloride, Bicarbonate, Blood Urea Nitrogen, Creatinine, Glucose, total bilirubin, alkaline phosphatase, AST (SGOT), ALT (SGPT).
- Two 10mL K2 EDTA tubes of blood will be collected for banking at baseline and follow-up, which is optional and determined at the time of consent
- Critical laboratory values will be reported to the PI who will communicate with the participant.

### **6.6.3 Laboratory assessments (other)**

The following laboratory studies will be obtained at specified intervals while on study:

Correlative research labs (refer to **section 10.0**)

### **6.6.4 Physical function assessments**

Physical performance will be objectively assessed using the Short Physical Performance Battery (SPPB). This validated measure comprises a short walk, repeated chair stands, and balance test. Submaximal (6-minute walk) exercise capacity will be measured to assess physical fitness. The 6-minute walk will be performed to assess fitness. Grip strength will be performed to calculate a Fried Frailty Index. These measures will be performed by trained research nurses per protocol in the CRU and at participating sites.

#### **6.6.5 Cognitive assessment**

Attention and perceptual speed will be measured with the Digital Symbol Substitution Test (DSST). Participants are presented a series of numbered symbols and then asked to draw the appropriate symbols below a list of random numbers. This will be conducted by trained study coordinators.

#### **6.6.6 Patient reported outcomes**

The PROMIS fatigue survey will be administered at baseline, 2, 4, 8, 12 weeks and the End of Treatment Visit (@ week 16). Other patient-reported outcomes will be administered at baseline and 12 weeks as outlined in the study calendar. If unable to come in person for follow-up study visit due to COVID-19 or other intercurrent event, patient reported data will be collected by phone.

### **6.7 Duration of Study Intervention**

Treatment with MGE will continue for 12 weeks or until one of the following criteria applies:

- Intercurrent illness that prevents further administration of treatment;
- Unacceptable adverse event(s) attributable to MGE;
- Patient misses more than 28 consecutive days of treatment for any reason;
- Participant takes Coumadin or Warfarin while on study
- Changes in the patient's condition render the patient unacceptable for further treatment in the judgment of the treating physician;
- Patient decides to withdraw from the study; or
- Patient is noncompliant, determined at the discretion of the principal investigator in conjunction with the treating physician

### **6.8 Duration of Follow Up**

Patients will be followed for toxicity/adverse events for 30 days after the last dose of the study drug.

Patients will be instructed to inform the study staff of any medical concerns that arise during the first 30 days after stopping the study drug for any reason. The study team will assess for toxicity/adverse events and determine attribution. Of note, a 24-hour washout period was adequate in the Phase 1 protocol with the same drug (CCCFU #01815, manuscript under review). Participants will also be called by the study team for the End of Treatment Assessment tele-visit 30 days after last study dose to review toxicity and assess resolution/stabilization of reported AEs.

Patients removed from the study intervention for unacceptable adverse events will be followed until resolution or stabilization of the adverse event. All participants who discontinue taking the study drug (see section 6.5) will be asked to continue study visits per protocol. If they are unable or unwilling to come to the CRU or participating site as planned, study staff will attempt to collect

fatigue and other QOL data by phone in lieu of study visits as long as consent is not withdrawn. All participants will be followed for the study outcomes until the end of the study.

## **6.9 Criteria for Removal from Study Intervention**

All patients will be expected to complete their 12-week study visit, unless they withdraw consent or are medically unable, even if they have stopped MGE. If they are unable or unwilling, they will be contacted by phone and asked to complete the survey-based data.

Patients will be removed from study intervention when any of the criteria listed in **section 6.7** apply.

## **7.0 Dosing Delays/Dose Modifications**

### **7.1 Missed doses**

If a dose of MGE/placebo is missed, the patient will be instructed to take his/her next dose as scheduled. Missed doses should not be added to the next dose.

If treatment must be held for any reason, it must be restarted within 28 days, or the patient will be removed from the study intervention. Unused pills will be collected at the follow-up study visit.

### **7.2 Dose modification**

There will be no dose-modifications on study. The patient can choose to discontinue MGE/placebo at any time. If necessary, MGE/placebo can be held for up to 28 days.

Subjects who notify the study team of potential grade 2 or higher study drug-related toxicity concerns will be contacted by the study PI for further information. Subjects will permanently discontinue the study drug for any attributable grade 4 toxicity. If participants experience grade 2 or 3 toxicity potentially attributable to study drug, dosing will be held and appropriate supportive care recommendations made. Subjects will be re-assessed weekly until toxicity has resolved to grade 0-1. If the subject continues to experience grade 2 or 3 toxicity, he/she will hold the study drug for up to 27 days, and the study team will again follow up with the patient to ensure toxicity has resolved to grade 0-1. If the toxicity persists beyond 27 days and is possibly attributable to the study drug, the study drug will be permanently discontinued. If the toxicity resolves to grade 0-1 within 27 days, the subject will restart the study drug. If the same grade 2 or higher possibly-attributable toxicity returns despite appropriate supportive care measures (ie diarrhea despite use of anti-diarrheal medication), the subject will permanently discontinue the study drug.

Guidelines for study drug discontinuation include 1) any attributable grade 4 toxicity, 2) any attributable grade 2 or 3 toxicity that does not resolve within 27 days or recurs upon re-initiation of study drug, 3) study drug not taken for >28 consecutive days for any reason.

Guidelines for holding MGE/placebo: 1) any attributable grade 2 or 3 toxicity; 2) participant experiences medical or personal concern that is not attributable to study medication but prohibits study drug administration (i.e. inability to swallow, hospitalization).

## 8.0 Adverse Events List and Reporting Requirements

### 8.1 Adverse Event List for MGE

Expected: Based on previous studies, minimal AEs are expected, which may include flatulence, diarrhea, nausea, dyspepsia, constipation, and abdominal pain.

### 8.2 Adverse Event Characteristics

- **CTCAE term (AE description) and grade:** The descriptions and grading scales found in the revised NCI Common Terminology Criteria for Adverse Events (CTCAE) version 5.0 will be utilized for AE reporting. All appropriate treatment areas should have access to a copy of the CTCAE version 5.0. A copy of the CTCAE version 5.0 can be downloaded from the CTEP web site (<http://ctep.cancer.gov>).
- **‘Expectedness’:** AEs can be ‘Unexpected’ or ‘Expected’ (see Section 7.1 above) for expedited reporting purposes only.
- **Attribution of the AE:**
  - Definite – The AE **is clearly related** to the study intervention.
  - Probable – The AE **is likely related** to the study intervention.
  - Possible – The AE **may be related** to the study intervention.
  - Unlikely – The AE **is doubtfully related** to the study intervention.
  - Unrelated – The AE **is clearly NOT related** to the study intervention.

### 8.3 STRC SAE Reporting Requirements

The Safety and Toxicity Reporting Committee (STRC) is responsible for reviewing SAEs for WFBCCC Institutional studies as outlined in Appendix D. All Adverse Events that occur during protocol intervention and are coded as either 1) **unexpected grade 4**, 2) **unplanned inpatient hospitalization > 24 hours (regardless of grade)**, or **grade 5 (death)** must be reported to the STRC using the SAE console in WISER. All WFBCCC Clinical Protocol and Data Management (CPDM) staff members assisting a Principal Investigator in investigating, documenting and reporting an SAE qualifying for STRC reporting are responsible for informing a clinical member of the STRC as well as the entire committee via the email notification procedure of the occurrence of an SAE.

### 8.4 WFUHS IRB AE Reporting Requirements

Any unanticipated problems involving risks to subjects or others and adverse events shall be promptly reported to the IRB, according to institutional policy. Reporting to the IRB is required regardless of the funding source, study sponsor, or whether the event involves an investigational or marketed drug, biologic or device. Reportable events are not limited to physical injury, but include psychological, economic and social harm. Reportable events may arise as a result of drugs, biological agents,

devices, procedures or other interventions, or as a result of questionnaires, surveys, observations or other interactions with research subjects.

All members of the research team are responsible for the appropriate reporting to the IRB and other applicable parties of unanticipated problems involving risk to subjects or others. The Principal Investigator, however, is ultimately responsible for ensuring the prompt reporting of unanticipated problems involving risk to subjects or others to the IRB. The Principal Investigator is also responsible for ensuring that all reported unanticipated risks to subjects and others which they receive are reviewed to determine whether the report represents a change in the risks and/or benefits to study participants, and whether any changes in the informed consent, protocol or other study-related documents are required.

Any unanticipated problems involving risks to subjects or others occurring at a site where the study has been approved by the WFUHS IRB (internal events) must be reported to the WFUHS IRB within 7 calendar days of the investigator or other members of the study team becoming aware of the event.

Any unanticipated problems involving risks to subjects or others occurring at another site conducting the same study that has been approved by the WFUHS IRB (external events) must be reported to the WFUHS IRB within 7 calendar days of the investigator or other members of the study team becoming aware of the event.

Any event, incident, experience, or outcome that alters the risk versus potential benefit of the research and as a result warrants a substantive change in the research protocol or informed consent process/document in order to insure the safety, rights or welfare of research subjects.

## **8.5 Sponsor Reporting Requirements**

This study has no third part sponsor. This study is funded by a CTSI pilot grant.

## **9.0 Pharmaceutical Information**

Muscadine grape extract is a nutraceutical compound.

A list of the adverse events and potential risks associated with the investigational agents administered in this study can be found in Section 8.

### **9.1 Pharmaceutical/Device Accountability**

Patients will be instructed to return their pill bottles and remaining pills at each study visit. Drug accountability logs will be maintained by the Wake Forest Investigational Drug Services for the investigative agent (MGE) used under this protocol. These logs shall record quantities of study drug received and quantities dispensed to patients, including lot number, date dispensed, patient identifier number, protocol number, dose, quantity returned, balance remaining, and the initials of the person dispensing the medication.

### **9.2 Muscadine Grape Extract (MGE)**

**Product description:** This pilot study uses a specific formulation of muscadine grape extract (MGE) produced by Piedmont Research & Development Corporation from a powdered extract obtained from NPC Corporation, formerly known as Nature's Pearl (Advance, NC). The same product was used for a phase 1 study in participants with advanced cancer (FDA IND 128937; clinicaltrials.gov NCT02583269) and a phase 2 study in participants with prostate cancer (FDA IND 139288; clinicaltrials.gov NCT03496805).

The muscadine grapes are pressed and processed on site per good manufacturing practice (FDA Code of Federal Regulations 21). The extract is dried and converted to powder at Pharmachem Laboratories, Inc. (Kearny, New Jersey). The MGE is encapsulated with a vegetable capsule of hypromellose, bottled, and labeled at Clinical Encapsulation Services (CES) (Schenectady, NY). Quality control testing for microbial contamination (aerobic count, yeast and mold, E.coli/coliform, staph aureus, enterobacteriaceae, and salmonella) and phenolic levels occurs numerous times during the production process. Stability testing for both microbial contamination and phenolic levels will continue at regular intervals until the study is complete.

**Storage requirements:** Capsules should be stored at room temperature.

**Route of administration:** MGE is available for oral administration.

## 10.0 Correlative/Special Studies

Blood: To be collected at baseline, and 12 weeks. Approximately 20 mL of blood will be collected into an EDTA tube to measure cytokines and growth factors, including interleukin 6 (IL-6), tumor necrosis factor-alpha (TNF- $\alpha$ ), C reactive protein (CRP), HGF, and polymorphonuclear neutrophils (PMNs) to measure mitochondrial function. Samples will be collected by CRU or participating site nursing staff according to a protocol they establish with the study team. Samples will then be transported on ice to the Cell & Molecular Biology Core in the Hypertension Center at BioTech Place ([name]), using a commercial courier service. Samples will be stored at -80°C in the Hypertension Center (3rd Floor, BioTech Place) indefinitely until batched analysis. Analysis will take place in the Cell & Molecular Biology Core.

Two 10mL K2 EDTA tubes of blood will be collected for banking at baseline and follow-up, which is optional and determined at the time of consent.

Urine: At least 20 mL of urine will also be collected at baseline and follow-up for 8-OH deoxyguanosine levels and urolithin A glucuronide (UAG), stored at -80°C indefinitely until batched analysis. Samples will be transported on ice using commercial courier service to the Cell & Molecular Biology Core in the Hypertension Center at BioTech Place ([name]).

Stool samples: Fecal specimens will be collected at baseline and at ~12 weeks using an at-home fecal sampling kit. Two kits will be provided to participant at baseline, with detailed instructions for how and when to collect stool at home. Participants will be asked to mail samples in a pre-paid package to the laboratory. DNA will be isolated from fecal samples using the Qiagen DNeasy PowerSoil Pro kit protocol. Metagenomic sequencing will be performed by CosmosID Inc. (Rockville, MD). In brief, DNA libraries will be prepared using the Illumina Nextera XT library preparation kit, with a modified protocol. Library quantity will be assessed with Qubit (ThermoFisher). Libraries will be sequenced on an Illumina HiSeq platform 2x150bp. Fecal samples will be read at 12M read-depth. Unassembled sequencing

Pilot study of muscadine grape extract to improve fatigue among older adult cancer survivors (FOCUS)  
Wake Forest Baptist Comprehensive Cancer Center  
WFBCCC #98320

reads will be directly analyzed by CosmosID bioinformatics platform for multikingdom microbiome analysis and quantification of organism's relative abundance. Fecal microbiomes will be assessed by metagenomic sequencing and bioinformatics. A list of all the microbiologic species will be recorded, along with their relative abundance recorded as a % relative abundance of the total microbiome.

## 11.0 Data Management

Item/Form	Location
Informed consent document	WakeOne
Protocol registration & race/ethnicity verification	OnCore
Study visit data collection forms: Baseline, week 12	REDCap*
Medications and supplements	OnCore
Labs	REDCap*
Correlative labs	REDCap*
Adverse event ascertainment	REDCap*
Pre-toxicity and adverse events log	REDCap*
Patient surveys	REDCap*
Cognitive/Physical function & fitness forms	REDCap*
Telephone surveys	REDCap*
Off-treatment/Off-study form	REDCap*/OnCore

\*This project will utilize REDCap Clinical Data Interoperability Services. This is a special feature for importing data into REDCap from WakeOne. It provides an adjudication process whereby REDCap users can approve all incoming data from WakeOne before it is officially saved in their REDCap project. REDCap Clinical Data Interoperability Services can only be enabled by a REDCap administrator who serves as an honest broker to PHI. REDCap's Clinical Data Interoperability Services can only be accessed by users with valid WakeOne credentials. Using the Clinical Data Interoperability Service requires using the Medical Record Number (MRN) as a key to automatically gather demographics and laboratory data and reduces data entry errors.

## 12.0 Statistical Considerations

### 12.1 Analysis of Primary Objective

To address the primary objective, we will use a mixed effects model with a constraint of a common baseline mean across treatment groups and an unstructured covariance matrix to model all fatigue measures over time, and use linear contrasts to estimate the difference in change and corresponding 90% confidence interval between the two groups from baseline to follow-up. All outcomes will be measured even if the participants discontinue the intervention, to provide an estimate of effectiveness.

### 12.2 Analysis of Secondary Objectives

For secondary outcomes listed in Objective 2.2.1, 2.2.2, and 2.2.3, which are based on baseline and follow-up measures, we will estimate 95% confidence intervals for the differences between the two

groups for the secondary outcomes at 12 weeks. We will also fit a ANCOVA model adjusted for the baseline value of the outcome to each secondary outcome.

### **12.3 Analysis of Exploratory Objectives**

To analyze the biomarker outcomes in Objective 2.3.1, which are measured continuously, we will also use the ANCOVA approach described for the secondary objectives, and will construct 95% for the differences in the change between the two groups at 12 weeks.

To meet Objective 2.3.2, we will examine the proportion of different bacteria taxa at each time point, and will use a marginalized two-part beta regression model to account for the compositional nature of the data. If we are unable to fit this model, we will examine changes using McNemar-Bowker tests for within-person changes and for mammary and gut composition at 12 weeks.

To meet Objective 2.3.3, we will include the biomarker data in the models of the primary and secondary outcomes described above, and evaluate if the effects of the intervention on each outcome is attenuated in the presence of the biomarker. Attenuation of 10% or more in the intervention parameter estimate will indicate potential mediation in the presence of a clinically meaningful change of both the primary or secondary outcome and the biomarker of interest.

For Objective 2.3.4, we will compare the change in the DSST score between the 2 groups at 12 weeks, using a mixed model with linear contrasts.

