oxidative stress and thus may effectively prevent tissue damage from oxidative stress to reduce fatigue. 4T1 Triple negative breast cancer cells were injected into the mammary fat pad of 6-week-old female Balb/c mice. After 2 weeks, tumors were surgically removed and mice received either drinking water or 0.1 mg phenolics/mL of MGE in the drinking water. Mice were sacrificed after 4 weeks; tissues and fecal samples were collected for analysis. Alpha diversity (**Figure 10**) and the Firmicutes to Bacteroidetes ratio (**Figure 11**) were significantly increased in MGE-treated mice compared to the control, indicating enhanced microbial richness and increased energy harvest by the gut microbiome could improve symptoms of fatigue. Butyrate-producing bacteria, such as *Ruminococcus*, *Butyrivibrio* and *Lachnospiraceae*, were increased with MGE ( $p<0.05$ ) as well as the anti-inflammatory compound butyrate compared to other short-chain fatty acids ( $25.0 \pm 2.7\%$  vs  $75.3 \pm 15.5\%$ ;  $p<0.01$ ). Of note, the MGE supplement is a complex mixture of polyphenols that are further metabolized by the host cells or the gut microbiome to secondary and tertiary metabolites, including short chain fatty acids. **These metabolites may serve as additional energy sources, feeding directly into the TCA cycle and leading to enhanced energy production by the mitochondria, to reduce fatigue.**

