## **2.3 Exploratory Objectives**

- 2.3.1 To explore whether MGE administration alters 8-hydroxy-2 deoxyguanosine, peripheral blood mitochondrial function, IL-6, TNF-alpha, C-reactive protein, hepatocyte growth factor from baseline to 12 weeks compared to the placebo arm.
- 2.3.2 To explore whether MGE administration alters the microbiome from baseline to 12 weeks compared to the placebo arm.
- 2.3.3 To explore whether 8-hydroxy-2 deoxyguanosine, peripheral blood mitochondrial function, IL-6, TNF-alpha, C-reactive protein, hepatocyte growth factor and the microbiome may mediate changes in self-reported fatigue and physical function, fitness and activity from baseline to 12 weeks.
- 2.3.4 To explore whether MGE administration causes changes in cognitive speed (Digital Symbol Substitution Test) from baseline to 12 weeks compared to placebo.

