### **5.3. Exploratory outcomes**

- 5.3.1 Peripheral blood will be collected at the baseline and week 12 study visit, and will be processed to obtain serum for the measurement of cytokines including interleukin 6 (IL-6), tumor necrosis factor-alpha (TNF- $\alpha$ ), C reactive protein (CRP) and HGF and polymorphonuclear neutrophils (PMNs) to measure mitochondrial function. Cytokines and 8-OHdG will be measured using human ELISA kits (Abcam) and mitochondrial function will be assessed using a Seahorse XF Cell Mito Stress Test (Agilent).
- 5.3.2 Urine will be collected at baseline and 12 weeks to measure the oxidative stress marker 8-OHdG and urolithin A glucuronidate (UAG), a marker for the ingestion/metabolism of MGE. UAG, which is generated from the ingestion of MGE polyphenolic ellagitannins, will be measured using an LCMS-8050 triple quadrupole mass spectrometer in the Wake Forest School of Medicine Proteomics and Metabolomics Shared Resource.
- 5.3.4 Fecal specimens will be collected at baseline and at ~12 weeks using an at-home fecal sampling kit. Samples will be collected by the patient prior to the initiation of intervention and again near the completion of intervention. Patients will be asked to mail samples in a pre-paid package to the laboratory. DNA will be isolated from fecal samples using the Qiagen DNeasy PowerSoil Pro kit protocol. Metagenomic sequencing will be performed by CosmosID Inc. (Rockville, MD). In brief, DNA libraries will be prepared using the Illumina Nextera XT library preparation kit, with a modified protocol. Library quantity will be assessed with Qubit (ThermoFisher). Libraries will be sequenced on an Illumina HiSeq platform 2x150bp. Fecal samples will be read at 12M read-depth. Unassembled sequencing reads will be directly analyzed by CosmosID bioinformatics platform for multikingdom microbiome analysis and quantification of organism's relative abundance. Fecal microbiomes will be assessed by metagenomic sequencing and bioinformatics. A list of all the microbiologic species will be recorded, along with their relative abundance recorded as a % relative abundance of the total microbiome.
- 5.3.5 Digit Symbol Substitution Test (DSST) is a measure of attention and perceptual speed, amenable to change with exercise or fatigue in which participants are given a

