## 6.0 Intervention Plan

### 6.1 Study-Related Activities

Measures / Timepoints	Pre-Study a	Baseline	Wk 2	Wk 4	Wk 8	Wk 12	End of Trtmt Visit h
Informed consent	X						
Medical and oncologic history	X						
Concomitant medications assessed by self-report j	X	X	X	X	X	X g, j	
Karnofsky Self-Reported Performance Rating Scale		X					
Vital signs		X					X j
Adverse event assessment		X	X	X	X	X g, j	X
Drug dispensing b		X					
Pill count							X g, j
Telephone follow-up c			X	X	X		
Cognitive/Physical function & fitness (DSST, SPPB, 6-min walk, grip strength)		X					X j
CBC with differential d	X						X j
Serum chemistries d	X						X j
(Partially fasting) labs for phenolic levels (blood and urine) e		X					X j
(Partially fasting) labs for correlative studies e (blood and urine)		X					X j
Stool sample collection f		X					X j
PROMIS Fatigue survey		X	X	X	X	X g, j	X
Other patient reported outcomes (PAT-D, LASA, PROMIS Global Health, CES-D, MLTA, Self-reported weight loss) j		X					X g, j
Participant Feedback							X i, j

a Labs to assess eligibility must be completed within 30 days prior to the first dose of MGE/placebo.

b Study drug (MGE or placebo) will be dispensed as a 90-day supply at the baseline visit.

c Adherence and symptom review will be assessed at each study visit. In addition, participants will be contacted by phone as follows,  $\pm 3$  days: Wk2, Wk4, Wk8.

d Safety laboratory assessments must be done within 30 days of first dose of MGE/placebo and then on the study visits indicated. These labs include:

Complete blood count (CBC) with differential: WBC count with differential, platelet count, hemoglobin/hematocrit.

Serum chemistries (complete metabolic panel, CMP): sodium, potassium, chloride, bicarbonate, blood urea nitrogen, creatinine with creatinine clearance, glucose, aspartate aminotransferase (AST), alanine aminotransferase (ALT), total bilirubin, alkaline phosphatase.

e Phenolic levels and other research labs will be obtained at baseline, and 12 weeks ( $\pm 14$  days). Patients are asked to avoid coffee, tea, fruit juice, fruit, chocolate or wine after midnight prior to blood draw.

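### The fallback analysis for the exploratory microbiome objective is a paired test that cannot compare MGE with placebo, and it names mammary composition although stool is the only microbiome specimen

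*Combined protocol and SAP*

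**What the plan says.** Objective 2.3.2 in Section 2.3 is a randomised comparison: "To explore whether MGE administration alters the microbiome from baseline to 12 weeks compared to the placebo arm".

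Section 12.3 gives two rules for it. The first choice is a marginalised two-part beta regression on the proportions of bacterial taxa. If that model cannot be fitted, "we will examine changes using McNemar-Bowker tests for within-person changes and for mammary and gut composition at 12 weeks".

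The rules around it in Section 12.3 are explicit about arms. Biomarkers under Objective 2.3.1 are analysed by ANCOVA, with intervals "for the differences in the change between the two groups at 12 weeks". For Objective 2.3.4, "we will compare the change in the DSST score between the 2 groups at 12 weeks".

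On the data, Section 5.3 states "Fecal specimens will be collected at baseline and at ~12 weeks using an at-home fecal sampling kit", and Section 10.0 adds "Two kits will be provided to participant at baseline, with detailed instructions for how and when to collect stool at home". The calendar in Section 6.1 lists "Stool sample collection" and no other microbiome sample. Sections 5.3 and 10.0 say that the species found will be listed, each with its percentage share of the total microbiome.

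**The concern.** Three features of the fallback do not fit the objective or the data.

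- **No treatment contrast.** The named test examines change within persons. Neither half of the sentence mentions MGE or placebo. The purpose of the second half, on composition at 12 weeks, is unclear. If it was meant as a comparison of arms, a paired test cannot compare two independent groups.
- **No categories.** The test needs the same set of categories at both time points. Relative abundance is a percentage, and the plan gives no cut-points.
- **No mammary sample.** Blood and urine are collected for other assays, but the microbiome is measured only in stool.

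If the fallback came into use, a significant result could be reported as an MGE effect although it shows only that participants changed over 12 weeks. With the arms pooled, a real difference in opposite directions could go unseen. The cut-points would also have to be chosen after the data were in hand.

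**Working it through.** The plan attaches no figure to this analysis, so there is none to reproduce. The check compares the text with what the test computes, then illustrates the consequence.

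**1. What the test computes.** For k categories, let n_ij be the number of participants in category i at baseline and j at week 12. The statistic is

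X² = Σ_{i<j} (n_ij − n_ji)² / (n_ij + n_ji), on k(k−1)/2 degrees of freedom.

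Treatment arm does not appear. The null hypothesis is that movements from i to j and from j to i are equally frequent, which differs from the null hypothesis of Objective 2.3.2.

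**2. A hand example with two categories.** Take 30 per arm, as in Section 12.4, and assume that in each arm a taxon's category rises in 35% of participants and falls in 10%. MGE then has no effect. The pooled expected counts are 60 × 0.35 = 21 rises and 60 × 0.10 = 6 falls. Then X² = (21 − 6)² / (21 + 6) = 225/27 = 8.33 on 1 degree of freedom, p about 0.004.

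Now reverse the placebo arm (10% rise, 35% fall), so that the arms differ strongly. Pooled rises are 30 × 0.35 + 30 × 0.10 = 13.5 and pooled falls are also 13.5, so X² = 0.

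**3. The same two-category setting by simulation** (exact McNemar test, 3,000 runs, two-sided 0.05, identical arms):

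| Rise / fall in both arms | Within MGE arm | Pooled | Between-arm Fisher test |
|---|---|---|---|
| 25% / 10% | 19% | 43% | 2% |
| 35% / 10% | 44% | 80% | 3% |
| 40% / 5% | 82% | 99% | 3% |

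**4. Continuous abundance cut into categories.** The assumptions are log-normal abundance without zeros, baseline to week 12 correlation 0.3, 0.5 or 0.7, tertiles of baseline, arms pooled, two-sided 0.05 and 2,000 runs per setting. Only the 30 per arm comes from the plan. Three entries in a cell correspond to the three correlations.

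| Shift (SD) | McNemar-Bowker, pooled | Rank-sum on change, between arms |
|---|---|---|
| Equal, 0.3 | 23% / 28% / 40% | 4% to 5% |
| Equal, 0.5 | 56% / 71% / 86% | 4% to 5% |
| Opposite, 0.3 | 4% / 4% / 3% | 40% / 54% / 74% |
| Opposite, 0.5 | 5% / 4% / 5% | 81% / 91% / 99% |

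With 2 or 4 categories in place of 3, McNemar-Bowker rejects in 15% to 83% (equal shifts) and 3% to 5% (opposite shifts). Repeat runs move the equal-shift range by a few percentage points, mostly at its lower end.

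The plan does not say whether the test would be pooled. Run in the MGE arm alone with tertiles, it rejects in about 8% to 42% when placebo shifts equally.

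**5. The mammary reference.** Sections 5.3, 6.1 and 10.0 provide for stool only, and eligibility in Section 3.1 covers many solid tumours and blood cancers. In the text available for review, the only other use of the word is in the preclinical background, where tumour cells were "injected into the mammary fat pad of 6-week-old female Balb/c mice".

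**The case against.** The best defence is that the fallback is read too strictly. The beta-regression sentence names no arm contrast either, and there the comparison is taken from the objective; the fallback could be given the same benefit. The species list yields presence or absence, a natural two-category outcome, so the data can supply categories. Rejecting when both arms truly change is correct behaviour for a within-person test. The 0.3 to 0.5 SD shifts have no source in the plan, and assuming no zeros sits poorly with the choice of a two-part model. The masking of opposite changes depends on pooling: run in one arm, the test rejects in about 11% to 39% under opposite shifts.

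Much of this is fair. Silence about arms is weak evidence by itself, the categories are unstated rather than impossible, and the percentages are illustrative. The main point survives. A beta regression can carry a treatment term, whereas McNemar-Bowker cannot, whatever the categories and whether pooled or run by arm. Significance in one arm and not in the other is also not a test of the difference between them. Mammary may be a simple slip, but deleting it does not supply the missing contrast.

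**Conclusion.** The concern holds and is minor. Section 12.3 names a fallback that cannot answer Objective 2.3.2 as written, because the test ignores treatment assignment. It also cannot be carried out in full, because categories are not defined and no mammary specimen exists. These conclusions rest on the text and on the form of the test, not on the simulation.

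The practical size cannot be derived from the documents. Under the stated assumptions, the pooled test rejects far more often than 5% when there is no treatment effect, and at or below 5% when the arms move apart. The first-choice beta regression is not in question. The issue arises only if that model cannot be fitted, and no primary or secondary conclusion depends on it.

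**What to change.** Replace the fallback sentence in Section 12.3 with one named between-arm analysis of the stool data, for example: *If this model cannot be fitted, the baseline-to-week-12 change in each taxon's relative abundance will be compared between MGE and placebo with a Wilcoxon rank-sum test, using a permutation p-value.* Delete the reference to mammary composition.

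This needs no categories and no rule for replacing zeros, and the permutation deals with ties at zero. Other between-arm methods would also serve, such as a baseline-adjusted regression on transformed abundance, which would be closer to the ANCOVA used for Objective 2.3.1. What matters is that one method with an arm contrast is fixed before the unblinded data are analysed. If a categorical analysis is preferred, the categories must be defined and an arm comparison added.

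The cost is one sentence of wording and a standard test on samples already planned. A rank or permutation test may be somewhat less efficient than a well-fitting model, and the rank-sum test on raw change neither adjusts for baseline nor addresses the compositional structure.
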